Treatment Arm: Treatment A, Subject ID: XXXXXXXXXX, Age: xx, Sex: X, Race: XXXXXXXX

Treatment Administration: First Date: DDMONYYYY, Last Date: DDMONYYYY, Number of infusions: xx

X	XXXXXXXXXXXXXXXXXX/ XXXXXXXXXXXXXXXXXX	DDMONYYYY/ DDMONYYYY	xx	During	Related	2	Reduced	Ong.	xx
---	---	-------------------------	----	--------	---------	---	---------	------	----

Treatment Arm: Treatment B, Subject ID: XXXXXXXXXX, Age: xx, Sex: X, Race: XXXXXXXX

Treatment Administration: First Date: DDMONYYYY, Last Date: DDMONYYYY, Number of infusions: xx

X	XXXXXXXXXXXXXXXXXX/ XXXXXXXXXXXXXXXXXX	DDMONYYYY/ DDMONYYYY	xx	After	Unrelated	3	Interrupted	Res. w. sequ.	xx
---	---	-------------------------	----	-------	-----------	---	-------------	---------------	----

MedDRA version 19.1, NCI-CTCAE version 4.03.

Note: (a) Action: No change = Dose not changed, Reduced = Dose reduced, Interrupted = Drug interrupted, Withdrawn = Drug withdrawn, N/A = Not applicable.

(b) Outcome: Change = Change in severity, Res. = Resolved, Res. w. sequ. = Resolved with sequelae, Ong. = Ongoing, Fatal = Fatal, Unknown = Unknown.

Programming note: MedDRA version 19.1 or highest at time of data transfer.

15.3: Safety Data

15.3.5: Clinical Laboratory Evaluations

Table 15.3.5.1: Hematology - Shift from Baseline to Worst On-treatment Value - SAF Analysis Set

Laboratory Test	Treatment	Baseline Classification	Worst On-treatment Value				Total n (%)
			Low n (%)	Normal n (%)	High n (%)	Missing n (%)	
PARAM1 (Unit1)	Treatment A N=XXX	Low	xxx (xx.x)	xxx (xx.x)	xxx (xx.x)	xxx (xx.x)	xxx (100.0)
		Normal	xxx (xx.x)	xxx (xx.x)	xxx (xx.x)	xxx (xx.x)	xxx (100.0)
		High	xxx (xx.x)	xxx (xx.x)	xxx (xx.x)	xxx (xx.x)	xxx (100.0)
		Missing	xxx (xx.x)	xxx (xx.x)	xxx (xx.x)	xxx (xx.x)	xxx (100.0)
		Total	xxx (xx.x)	xxx (xx.x)	xxx (xx.x)	xxx (xx.x)	xxx (100.0)
	Treatment B N=XXX	Low	xxx (xx.x)	xxx (xx.x)	xxx (xx.x)	xxx (xx.x)	xxx (100.0)
		Normal	xxx (xx.x)	xxx (xx.x)	xxx (xx.x)	xxx (xx.x)	xxx (100.0)
		High	xxx (xx.x)	xxx (xx.x)	xxx (xx.x)	xxx (xx.x)	xxx (100.0)
		Missing	xxx (xx.x)	xxx (xx.x)	xxx (xx.x)	xxx (xx.x)	xxx (100.0)
		Total	xxx (xx.x)	xxx (xx.x)	xxx (xx.x)	xxx (xx.x)	xxx (100.0)
.....							

Note: Baseline is the last measurement prior to the first dose of any trial treatment.
Normal category includes low values for high parameters and high values for low parameters.

Repeat table 15.3.5.1 for:

Table 15.3.5.2: Clinical Chemistry - Shift from Baseline to Worst On-treatment Value - SAF Analysis Set

Programming Note: All parameters and treatments are reported.

- For Hematology: Hematocrit, Hemoglobin, Mean cellular hemoglobin, Mean cellular hemoglobin concentration, Mean cellular volume, Platelet count, Red blood cell count, Red cell distribution width, White blood cell count and differential.

- For Clinical Chemistry: Gamma glutamyl transferase, ALT, Albumin, AP, AST, Bilirubin – direct (only if total bilirubin is outside the normal range), Bilirubin – total, Calcium, Chloride, Bicarbonate, Serum creatinine, Glucose, Potassium, Protein – total, Sodium, Urea, Uric acid, C-reactive protein.

Worst value for non-CTCAE parameters need to be defined with the team for each parameter (e.g. Blood urea nitrogen high). In case worse value could be either low or high for some tests, then report both PARAM low and PARAM high (e.g. Hematocrit low and Hematocrit high).

In case, there is not enough space to display the table on one page, merge the columns for parameter and treatment arm.

15.3: Safety Data

15.3.5: Clinical Laboratory Evaluations

Table 15.3.5.3: Hematology - Shift in Toxicity Grading from Baseline to Highest Grade - SAF Analysis Set

Laboratory Test	Treatment	Baseline NCI-CTCAE Grade	Worst NCI-CTCAE Grade							Total n (%)
			Grade 0 n (%)	Grade 1 n (%)	Grade 2 n (%)	Grade 3 n (%)	Grade 4 n (%)	Missing n (%)		
PARAM1 (Unit1)	Treatment A N=xxx	Grade 0	xxx (xx.x)	xxx (xx.x)	xxx (xx.x)	xxx (xx.x)	xxx (xx.x)	xxx (xx.x)	xxx (xx.x)	xxx (100.0)
		Grade 1	xxx (xx.x)	xxx (xx.x)	xxx (xx.x)	xxx (xx.x)	xxx (xx.x)	xxx (xx.x)	xxx (xx.x)	xxx (100.0)
		Grade 2	xxx (xx.x)	xxx (xx.x)	xxx (xx.x)	xxx (xx.x)	xxx (xx.x)	xxx (xx.x)	xxx (xx.x)	xxx (100.0)
		Grade 3	xxx (xx.x)	xxx (xx.x)	xxx (xx.x)	xxx (xx.x)	xxx (xx.x)	xxx (xx.x)	xxx (xx.x)	xxx (100.0)
		Grade 4	xxx (xx.x)	xxx (xx.x)	xxx (xx.x)	xxx (xx.x)	xxx (xx.x)	xxx (xx.x)	xxx (xx.x)	xxx (100.0)
		Missing	xxx (xx.x)	xxx (xx.x)	xxx (xx.x)	xxx (xx.x)	xxx (xx.x)	xxx (xx.x)	xxx (xx.x)	xxx (100.0)
		Total	xxx (xx.x)	xxx (xx.x)	xxx (xx.x)	xxx (xx.x)	xxx (xx.x)	xxx (xx.x)	xxx (xx.x)	xxx (100.0)

Shell continues on the next page

15.3: Safety Data

15.3.5: Clinical Laboratory Evaluations

Table 15.3.5.3: Hematology - Shift in Toxicity Grading from Baseline to Highest Grade - SAF Analysis Set

Laboratory Test	Treatment	Baseline NCI-CTCAE Grade	Worst NCI-CTCAE Grade							Total n (%)
			Grade 0 n (%)	Grade 1 n (%)	Grade 2 n (%)	Grade 3 n (%)	Grade 4 n (%)	Missing n (%)		
	Treatment B N=xxx	Grade 0	xxx (xx.x)	xxx (xx.x)	xxx (xx.x)	xxx (xx.x)	xxx (xx.x)	xxx (xx.x)	xxx (xx.x)	xxx (100.0)
		Grade 1	xxx (xx.x)	xxx (xx.x)	xxx (xx.x)	xxx (xx.x)	xxx (xx.x)	xxx (xx.x)	xxx (xx.x)	xxx (100.0)
		Grade 2	xxx (xx.x)	xxx (xx.x)	xxx (xx.x)	xxx (xx.x)	xxx (xx.x)	xxx (xx.x)	xxx (xx.x)	xxx (100.0)
		Grade 3	xxx (xx.x)	xxx (xx.x)	xxx (xx.x)	xxx (xx.x)	xxx (xx.x)	xxx (xx.x)	xxx (xx.x)	xxx (100.0)
		Grade 4	xxx (xx.x)	xxx (xx.x)	xxx (xx.x)	xxx (xx.x)	xxx (xx.x)	xxx (xx.x)	xxx (xx.x)	xxx (100.0)
		Missing	xxx (xx.x)	xxx (xx.x)	xxx (xx.x)	xxx (xx.x)	xxx (xx.x)	xxx (xx.x)	xxx (xx.x)	xxx (100.0)
		Total	xxx (xx.x)	xxx (xx.x)	xxx (xx.x)	xxx (xx.x)	xxx (xx.x)	xxx (xx.x)	xxx (xx.x)	xxx (100.0)

Shell continues on the next page

15.3: Safety Data

15.3.5: Clinical Laboratory Evaluations

Table 15.3.5.3: Hematology - Shift in Toxicity Grading from Baseline to Highest Grade - SAF Analysis Set

Laboratory Test	Treatment	Baseline NCI-CTCAE Grade	Worst NCI-CTCAE Grade							Total n (%)
			Grade 0 n (%)	Grade 1 n (%)	Grade 2 n (%)	Grade 3 n (%)	Grade 4 n (%)	Missing n (%)		
	Treatment C N=xxx	Grade 0	xxx (xx.x)	xxx (xx.x)	xxx (xx.x)	xxx (xx.x)	xxx (xx.x)	xxx (xx.x)	xxx (xx.x)	xxx (100.0)
		Grade 1	xxx (xx.x)	xxx (xx.x)	xxx (xx.x)	xxx (xx.x)	xxx (xx.x)	xxx (xx.x)	xxx (xx.x)	xxx (100.0)
		Grade 2	xxx (xx.x)	xxx (xx.x)	xxx (xx.x)	xxx (xx.x)	xxx (xx.x)	xxx (xx.x)	xxx (xx.x)	xxx (100.0)
		Grade 3	xxx (xx.x)	xxx (xx.x)	xxx (xx.x)	xxx (xx.x)	xxx (xx.x)	xxx (xx.x)	xxx (xx.x)	xxx (100.0)
		Grade 4	xxx (xx.x)	xxx (xx.x)	xxx (xx.x)	xxx (xx.x)	xxx (xx.x)	xxx (xx.x)	xxx (xx.x)	xxx (100.0)
		Missing	xxx (xx.x)	xxx (xx.x)	xxx (xx.x)	xxx (xx.x)	xxx (xx.x)	xxx (xx.x)	xxx (xx.x)	xxx (100.0)
		Total	xxx (xx.x)	xxx (xx.x)	xxx (xx.x)	xxx (xx.x)	xxx (xx.x)	xxx (xx.x)	xxx (xx.x)	xxx (100.0)

NCI-CTCAE version 4.03.

Note: Baseline is the last measurement prior to the first dose of any trial treatment.

Repeat table 15.3.5.3 for:

Table 15.3.5.4: Clinical Chemistry - Shift in Toxicity Grading from Baseline to Highest Grade - SAF Analysis Set

Programming Note: Only gradable parameters are reported, examples are provided below – present all gradable parameters that are available.

- For Hematology: Leukocytes high (10E9/L), Leukocytes low (10E9/L), Hemoglobin high (g/L), Hemoglobin low (G/L), Platelets (10E9/L), Lymphocytes high (10E9/L), Lymphocytes low (10E9/L), Neutrophils (10E9/L)...

- For Biochemistry: Bilirubin (µmol/L), AST (U/L), ALT (U/L), Alkaline Phosphatase (U/L), Creatinine (µmol/L), Albumin (G/L), Calcium low (mmol/L), Calcium high (mmol/L), Sodium low (mmol/L), Sodium high (mmol/L), Potassium low (mmol/L), Potassium high (mmol/L), Glucose high (mmol/L), Glucose low (mmol/L), Uric acid high (mmol/L)...

[figure not shown]
In case there is not enough space to display the table on one page, merge the columns for parameter and treatment.

15.3: Safety Data

15.3.5: Clinical Laboratory Evaluations

Figure 15.3.5.5: Boxplot of Change from Baseline for ALT Values by Visit - SAF Analysis Set

Programming Note: Split figure across multiple pages as the number of weeks increases.

Programming note: The y-axis label should be "<PARAM> Change from Baseline (<units>). The x-axis label should be "Visit". For the partially unblinded outputs, the Treatment Group legend will show "Treatment A" etc.

Use only the following colors (applies to all figures): Cyan, Magenta, Yellow & Black. Also use different symbols for each treatment group.

Repeat figure 15.3.5.5 for:

Figure 15.3.5.6: Boxplot of Change from Baseline for AST Values by Visit - SAF Analysis Set

Figure 15.3.5.7: Boxplot of Change from Baseline for Total Bilirubin Values by Visit - SAF Analysis Set

Figure 15.3.5.8: Boxplot of Change from Baseline for Total White Blood Count Values by Visit - SAF Analysis Set

Figure 15.3.5.9: Boxplot of Change from Baseline for Neutrophils Values by Visit - SAF Analysis Set

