7.4.1 Adverse Events

7.4.1.1 Adverse Event Definitions

Adverse Event

An AE is any untoward medical occurrence in a subject or clinical investigation subject administered a pharmaceutical product, regardless of causal relationship with this treatment. An

AE can therefore be any unfavorable and unintended sign (including an abnormal laboratory finding), symptom, or disease temporally associated with the use of a medicinal product, whether or not considered related to the IMP.

A TEAE is defined as any event not present prior to the initiation of the IMP or any event already present that worsens in either severity or frequency following exposure to the IMP.

For surgical or diagnostic procedures, the condition/illness leading to such a procedure is considered as the AE rather than the procedure itself.

The Investigator is required to grade the severity or toxicity of each AE.

Investigators will reference the National Cancer Institute (NCI) - CTCAE, Version 4.03 (publication date: 14 June 2010), a descriptive terminology that can be used for AE reporting.

A general grading (severity/intensity; hereafter referred to as severity) scale is provided at the beginning of the above referenced document, and specific event grades are also provided.

If a particular AE's severity is not specifically graded by the guidance document, the Investigator is to use the general NCI-CTCAE definitions of Grade 1 through Grade 5 following his or her best medical judgment.

The 5 general grades are:

- Grade 1 or Mild
- Grade 2 or Moderate
- Grade 3 or Severe
- Grade 4 or Life-threatening
- Grade 5 or Death.

According to Sponsor convention, any clinical AE with severity of Grade 4 or 5 must also be reported as an SAE. However, a laboratory abnormality of Grade 4, such as anemia or neutropenia, is considered serious only if the condition meets one of the serious criteria described below.

If death occurs, the primary cause of death or event leading to death should be recorded and reported as an SAE. "Fatal" will be recorded as the outcome of this specific event and death will not be recorded as separate event. Only, if no cause of death can be reported (for example, sudden death or unexplained death), the death per se might then be reported as an SAE.

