7.4.1.3 Definition of the Adverse Event Reporting Period

The AE reporting period for safety surveillance begins when the subject is initially included in the trial (date of first signature of first informed consent) and continues through the post-treatment Safety Follow-up Period.

Any SAE assessed as related to IMP must be reported whenever it occurs, irrespective of the time elapsed since the last administration of IMP.

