8.3.3 Safety Endpoints

Safety endpoints in this trial include the following:

- The nature, incidence, severity, relationship, and outcome of AEs, SAEs, and AESIs from screening up to Week 116;
- Number of subjects with treatment-emergent AEs, SAEs, and AESIs from baseline up to Week 116;
- Treatment-emergent changes in clinical laboratory measures, ECGs, and vital signs from baseline up to Week 116;
- Incidence of subjects with positive ADA titers from baseline up to Week 116.

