8.5.3 Analysis of Secondary Endpoints

Analysis of Key Secondary Efficacy Endpoints

The key secondary endpoints will be tested for abituzumab 1500 mg versus placebo, using data for subjects on trial treatment, in the following order after the primary endpoint is met.

1. The Mahler TDI at Week 52 will be analyzed using a mixed-effects model adjusting for baseline FVC% predicted, duration of prior mycophenolate use at baseline, and Mahler BDI.
2. The absolute change in SGRQ total score at Week 52 will be analyzed using a mixed-effects model adjusting for baseline FVC% predicted, duration of prior mycophenolate use at baseline, and baseline SGRQ score.
3. The absolute change from baseline in mRSS at Week 52 in subjects with dcSSc at baseline will be analyzed using a mixed-effects model adjusting for baseline FVC% predicted, duration of prior mycophenolate use at baseline, and baseline mRSS.
4. The absolute change from baseline in QLF in the region of highest severity at Week 52 will be analyzed using an ANCOVA model adjusting for baseline FVC% predicted, duration of prior mycophenolate use at baseline, and baseline QLF.
5. Overall survival will be analyzed using a stratified log-rank test and presented by Kaplan-Meier estimates and 95% confidence interval, including the survival data available up to the analysis cut-off date. A Cox proportional hazards regression model will be used to obtain hazard ratios and 95% confidence intervals adjusting for baseline FVC% predicted and duration of prior mycophenolate use at baseline.

The mixed-effects model will include random intercept, treatment, and visit as fixed effect terms, treatment-by-visit as the interaction term, adjusting for baseline covariates. An unstructured covariance matrix will be used as the default option. Missing data is assumed MAR.

Missing data for binary endpoint will be imputed as non-responders.

Analysis of Other Secondary Efficacy Endpoints

CCI [REDACTED]

[REDACTED]

[REDACTED]

Analysis of Safety Endpoints

Adverse events will be summarized by treatment group, by severity, and by relationship to IMP. Serious AEs, AEs leading to treatment discontinuation, and AESI will be summarized by treatment group.

Summary statistics will be used to present changes from baseline in continuous laboratory and vital sign data. Shift tables will be used to present changes in categorical laboratory parameters. Figures may be generated to assist safety evaluation.

Analysis of Quality of Life Endpoints

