Listing 16.2.9.1: Vital Signs – SAF Analysis Set.....81
Listing 16.2.9.2: Electrocardiogram Data – SAF Analysis Set82

3 List of Abbreviations and Definition of Terms

Refer to the Study SAP.

4 Modification History

Unique Identifier for SAP Version	Date of SAP Version	Author	Changes from the Previous Version
1.0	05 April 2018	PPD	N/A – First version

5 Purpose of the Statistical Analysis Plan Addendum

The purpose of this statistical analysis plan (SAP) addendum is to document technical and detailed specifications for the Final Analysis for protocol EMR200017-014.

Due to the early termination of the study and consequently the limited number of subjects and data available, the full pre-planned analyses in the Study SAP (dated 15 November 2017) will not be carried out, since they may lead to unreliable conclusions. Hence this addendum references the applicable parts of the Study SAP and the Independent Data Monitoring Committee (IDMC) SAP (dated 29 June 2016) to produce the tables, listings, and figures (TLFs) to be included in the abbreviated clinical study report (CSR).

6 Summary of Clinical Study Features

Refer to the Study SAP.

7 Sample Size/Randomization

Refer to the Study SAP.

8 Overview of Planned Analyses

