8.1 Final Analysis

Cut-off date:

The data cut-off date for the final analysis will be when all randomized subjects have completed the Week 12 Safety Follow-up visit or been lost to follow-up. No more data are expected to be entered into the database by the sites after this point.

A blinded data review meeting will be held prior to database lock in order to identify and confirm protocol deviations (PDs).

Dissemination of results:

The blinded Biostatistics study team will become unblinded after database lock. Results will be generated on the aggregate group level and delivered to the Sponsor as one package (no key TLFs will be produced) following the normal process.

TLF Shells:

Refer to [Appendix 1](#) for the TLF shells.

9 Changes to the Planned Analyses in the Clinical Study Protocol

See subsequent sections regarding the analyses that will be performed for the abbreviated CSR.

10 Protocol Deviations and Analysis Sets

Refer to the Study SAP.

Subject disposition will use the Screening Analysis Set, all baseline and safety summaries will use the Safety Analysis Set and all efficacy summaries will use the mITT Analysis Set. The other analysis sets will not be required for the following reasons:

- Intent-to-treat – All randomized subjects were treated so this is equivalent to the mITT analysis set.
- Per-Protocol – The purpose of this was for sensitivity analysis on the primary and key secondary endpoints, which will no longer be performed.
- PK – No PK analyses will be performed for the abbreviated CSR.
- Pharmacogenetics – No CC1 analyses will be performed for the abbreviated CSR.

Since no supportive analyses on the primary endpoint will be performed, no subgroups will be identified.

11 General Specifications for Statistical Analyses

Refer to the Study SAP. Only summary statistics will be computed.

Early Termination Visit:

Since subjects will be performing their early termination (ET) visits at different stages within the protocol schedule of assessments, for the efficacy by-visit summaries, the ET visits will reference the protocol visits in between which they fell chronologically.

For example, if a subject performed their Week 12 visit, then performed their ET visit at a later date (but before their scheduled Week 24 visit), their ET visit will be shown as “ET (W12 – W24)” to display the weeks that it fell between.

Missing data:

No imputation of missing efficacy data or duration of prior mycophenolate use at baseline will be performed.

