Any trial treatment related grade >=3 treatment emergent AESI	xxx (xx.x)	xxx (xx.x)	xxx (xx.x)
Any trial treatment related grade >=4 treatment emergent AESI	xxx (xx.x)	xxx (xx.x)	xxx (xx.x)
Any treatment emergent AESI leading to death	xxx (xx.x)	xxx (xx.x)	xxx (xx.x)
Any trial treatment related treatment emergent AESI leading to death	xxx (xx.x)	xxx (xx.x)	xxx (xx.x)

NCI-CTCAE version 4.03.

Note: TEAEs are defined as events that start within the day of first dose of trial treatment until 28 days after last dose of treatment.

Related TEAEs are events with relationship missing, unknown or related.

AESI = Adverse Event of Special Interest.

15.3: Safety Data

15.3.1: Display of Adverse Events

Table 15.3.1.2: Overview of TEAEs Leading to Discontinuation / Dose Reduction of Treatment - SAF Analysis Set

Number of Subjects with:	Treatment A N=xxx (100%) n (%)	Treatment B N=xxx (100%) n (%)	Treatment C N=xxx (100%) n (%)
Any TEAE leading to temporary discontinuation of trial treatment	xxx (xx.x)	xxx (xx.x)	xxx (xx.x)
Any trial treatment related TEAE leading to temporary discontinuation of trial treatment	xxx (xx.x)	xxx (xx.x)	xxx (xx.x)
Any TEAE leading to permanent discontinuation of trial treatment	xxx (xx.x)	xxx (xx.x)	xxx (xx.x)
Any trial treatment related TEAE leading to permanent discontinuation of trial treatment	xxx (xx.x)	xxx (xx.x)	xxx (xx.x)
Any TEAE leading to dose reduction of trial treatment	xxx (xx.x)	xxx (xx.x)	xxx (xx.x)
Any trial treatment related TEAE leading to dose reduction of trial treatment	xxx (xx.x)	xxx (xx.x)	xxx (xx.x)

Note: TEAEs are defined as events that start within the day of first dose of trial treatment until 28 days after last dose of treatment.
Related TEAEs are events with relationship missing, unknown or related.

15.3: Safety Data

15.3.1: Display of Adverse Events

Table 15.3.1.3: TEAE by Primary System Organ Class (SOC) and Preferred Term (PT) - SAF Analysis Set

Primary System Organ Class Preferred Term	Treatment A N=xxx (100%) n (%)	Treatment B N=xxx (100%) n (%)	Treatment C N=xxx (100%) n (%)
Subjects with at least one event	xxx (xx.x)	xxx (xx.x)	xxx (xx.x)
SOC1	xxx (xx.x)	xxx (xx.x)	xxx (xx.x)
PT11	xxx (xx.x)	xxx (xx.x)	xxx (xx.x)
PT12	xxx (xx.x)	xxx (xx.x)	xxx (xx.x)
PT13	xxx (xx.x)	xxx (xx.x)	xxx (xx.x)
SOC2	xxx (xx.x)	xxx (xx.x)	xxx (xx.x)
PT21	xxx (xx.x)	xxx (xx.x)	xxx (xx.x)
PT22	xxx (xx.x)	xxx (xx.x)	xxx (xx.x)

MedDRA version 19.1.

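### The addendum's by-arm adverse event tables stop 28 days after the last dose, so they leave out most of the Safety Follow-up that the protocol's Week 116 endpoint covers, and the addendum does not declare this as a change

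*SAP*

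**What the plan says.** **The addendum.** Tables 15.3.1.1, 15.3.1.2, 15.3.1.3 and 15.3.1.8 carry the footnote: "TEAEs are defined as events that start within the day of first dose of trial treatment until 28 days after last dose of treatment". The remaining 15.3.1.x tables are built by repeating shells 15.3.1.3 or 15.3.1.8, so they inherit the rule. They include serious TEAEs (15.3.1.5) and AESIs (15.3.1.14). Every by-arm AE table in that series is a TEAE table. The cut-off in section 8.1 is later: "The data cut-off date for the final analysis will be when all randomized subjects have completed the Week 12 Safety Follow-up visit", or have been lost to follow-up. Section 9, on changes to the protocol's planned analyses, reads in full: "See subsequent sections regarding the analyses that will be performed for the abbreviated CSR". Section 17 leaves the safety summaries to the IDMC SAP.

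**The protocol.** Section 7.4.1.1 gives a definition with no closing date: "A TEAE is defined as any event not present prior to the initiation of the IMP or any event already present that worsens" in severity or frequency after exposure. Section 7.4.1.3 says that AE reporting "continues through the post-treatment Safety Follow-up Period". Section 8.3.3 lists as an endpoint: "Number of subjects with treatment-emergent AEs, SAEs, and AESIs from baseline up to Week 116". Section 8.5.3 adds: "Serious AEs, AEs leading to treatment discontinuation, and AESI will be summarized by treatment group".

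**The concern.** The trial pays for 12 weeks of safety observation after treatment, waits for it to finish, and then leaves most of it out of every by-arm AE count. A reader comparing arms in the abbreviated report would take the TEAE, serious TEAE and AESI tables as the protocol's safety endpoint, which they are not. To obtain that endpoint, the reader would have to count follow-up events from subject listings.

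The addendum is open about its other reductions. It gives a reason for each analysis set it drops, and it says that there will be no imputation of efficacy data, no tests and no confidence intervals. It does not identify the AE window as differing from the protocol. Section 5 gives a general reason: "Due to the early termination of the study and consequently the limited number of subjects and data available", the full analyses could mislead. That explains dropping models and tests. It does not explain why a descriptive count should end at 28 days.

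**Working it through.** **Inputs**

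- TEAE window: first dose to last dose + 28 days (addendum 18.1).
- Last planned dose: Week 100 (protocol 6.2).
- Safety Follow-up: 12 weeks = 84 days, with visits at 4 and 12 weeks (protocol 5.1, 7.1.3).
- Early termination (ET) visit: within 14 days of IMP discontinuation. Subjects who withdraw from the treatment period then enter the Safety Follow-up (protocol 7.1.3).
- Assumption: the gap *d* in days from last dose to ET visit. The documents do not fix it.

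**Reproducing the plan's horizon.** Trial day = 1 + 7 × week. Week 100 is Day 701 and Week 104 is Day 729, as in the schedule of assessments. 104 + 12 = Week 116, which is Day 813. The 6-week screening gives 6 + 104 + 12 = 122 weeks, as the protocol states.

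**On-schedule completer.** The window ends on Day 701 + 28 = Day 729, the day of the Week 104 visit. Follow-up runs from Day 729 to Day 813, so 84 of 84 days lie outside. If the last dose is 5 days late and the Week 104 visit 5 days early, 10 days are covered and 74 of 84 (88%) lie outside.

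**Subject entering follow-up from an ET visit.** Days outside = 84 − max(0, 28 − *d*).

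| *d* (days) | Days outside | Share of follow-up |
|---|---|---|
| 0 | 84 − 28 = 56 | 67% |
| 7 | 84 − 21 = 63 | 75% |
| 14 | 84 − 14 = 70 | 83% |
| 21 | 84 − 7 = 77 | 92% |
| 28 or more | 84 | 100% |

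If discontinuation is dated to the last dose, *d* is 0 to 14. If it is decided up to 28 days into a dosing interval, *d* can reach 28 + 14 = 42.

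Measured from the ET visit, the window closes at 28 − *d* days, never later than the nominal Week 4 follow-up visit. The 56 days between the Week 4 and Week 12 visits are therefore nominally outside for every such subject. With *d* = 0 and a Week 4 visit held 5 days early, up to 5 of those days fall inside.

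**Which case matters here.** The trial stopped early and the addendum is dated 5 April 2018. If no dose was given after that date, a Week 100 dose needs a first dose by 5 April 2018 − 700 days = 5 May 2016. The planned first-subject date was March 2016, so few subjects can be completers and the ET rows are the main case.

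**Other paths.** Subjects who stop IMP but stay on the visit schedule have a longer uncounted stretch, which depends on when they stopped. Subjects who withdraw from the trial contribute no follow-up visits.

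**Where late events still appear.**

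- Listings 16.2.7.1 and 16.2.7.2 show all AEs and SAEs with start dates.
- Table 15.3.2.1 counts deaths by arm with no stated window.
- Table 15.1.1.1 counts trial withdrawals for AE by arm.
- The tables on discontinuation and dose reduction (15.3.1.2, 15.3.1.11, 15.3.1.12) are barely affected.

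**The case against.** There are four serious counter-arguments.

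- **Unseen documents.** The addendum depends on the Study SAP (15 November 2017) and the IDMC SAP (29 June 2016), neither of which was available. Either may define the 28-day window and justify it. This stands as a limit on the disclosure point. It does not change what the addendum's tables count.
- **A coherent choice, openly printed.** The rule stands under the parent shells. It matches the exposure formula in Table 15.3.0.1, which adds 28 days, one dosing interval, to the last infusion. A 28-day table is a sensible on-treatment summary, and a longer window takes in events after IMP has stopped or other therapy has begun. This is a reason to keep the 28-day tables. It does not make them the Week 116 endpoint: for an on-schedule completer the window closes at Week 104.
- **Little practical effect.** The trial is small, the report is abbreviated, and every AE and SAE is listed by treatment group. No data are lost, and nothing in the documents shows that a conclusion would change. All of this is true, and it limits the weight of the point. By-arm safety counts are nevertheless a main product of such a report.
- **The listing mark is harmless.** Listing 16.2.7.2 gives pre-dose and follow-up SAEs the same non-treatment-emergent mark, but the printed trial day already separates them. This is right, and the point does not depend on the mark.

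**Conclusion.** The concern holds. Followed as written, the by-arm tables of AEs, SAEs and AESIs do not deliver the protocol endpoint to Week 116, and the addendum does not say so. Between 67% and 100% of Safety Follow-up time lies outside the window for subjects who enter it from an ET visit, depending on the assumed gap from last dose to that visit. For an on-schedule completer the figure is 100% (88% at the limit of the visit windows). For subjects who left treatment early, Week 116 is read here as the end of their own Safety Follow-up.

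These figures describe time at risk, not events; how many events are affected cannot be learned from the documents. The mismatch between the texts is certain. Whether a reason is recorded in the Study SAP or IDMC SAP remains open. This is a gap in summary and disclosure, not a loss of data, and it should be fixed because a named endpoint is undelivered and the repair is cheap.

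**What to change.** 1. Keep the existing tables and label them as covering events that start up to 28 days after the last dose.
2. Add three by-arm tables, for AEs, SAEs and AESIs, covering first dose to the end of each subject's Safety Follow-up.
3. State in section 9 that the 28-day window differs from the protocol endpoint, and why. If the Study SAP or IDMC SAP already gives the reason, cite it there.
4. Optionally, mark follow-up events separately from pre-dose events in Listings 16.2.7.1 and 16.2.7.2.

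The cost is three tables from existing shells, a sentence in section 9 and, if wanted, one listing flag. No new data are needed. The added counts will include some events that start after IMP was stopped or other therapy begun; the retained 28-day tables let the reader separate these.
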